Study Design. Participation starts with a simple information sheet, online eligibility survey, orientation webinar, e-consent, and then another survey to collect baseline assessment data. Eligible participants will then complete an on-boarding process, which includes MyFitnessPal and scale set up. Participants will then be randomized (stratified by gender) and complete an 8-week intervention, and then two assessments at 9-weeks (weigh-in, survey) and 12-weeks (weigh-in).

Recruitment. We will post online recruitment ads that will contain a link to a simple information sheet and an online survey containing the screening questions. Ads that are done with Build Clinical will lead the participants to a landing page that will give them some more information about the study and then will have the link to bring them to the simple information sheet and survey. See the recruitment section (starting on page 6) for full recruitment details.

Screening. Participants will complete screening procedures online since they may be located anywhere in the country. The screening survey will first have a description of the study and the data we will collect from them at that point (the simple information sheet). At the bottom of the information sheet, they can mark whether they are interested in participating or not

interested. If they mark that they are interested, it will bring them to the screening questions to determine eligibility. The survey logic within REDCap will determine eligibility for participation based on participant responses. BuildClinical also had logic to determine eligibility. If they are ineligible, they will be notified after the survey is submitted. If they are eligible to proceed, they will be contacted by the study team via email to book a time to attend a live informational webinar.

We will not require PCP approval since we assess exclusionary medical conditions during the screening process. If conditions are reported that might put the participant at risk during the intervention, they will be excluded.

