After the BMI has been confirmed, UConn staff will do a final eligibility check, going through all previous steps done by the participant and double-check to confirm that they are eligible. If they are not, UConn staff will notify them via email. If they are eligible, UConn staff will engage in a series of emails with the participants to help them set-up the study app and confirm they are working. If the participant prefers, the set-ups can be done over the phone as well.

Participants will need to complete both surveys (screening and baseline), webinar, consent, setup the scale and provide the study team with a baseline weight to confirm BMI (done with scale we ship to them), and set-up all study apps before being randomized into the trial. Participants will be randomized into one of two groups.

Ineligible participants will be notified either automatically or by the research assistant/coordinator via email that they do not meet criteria for the study. Staff will use a generic response about how their pattern of responses does not match our eligibility criteria (the examples are provided in additional documentation). If they want to know specifics as to why they were ineligible, staff will refer the participant to email the PI so they can have a more detailed discussion about eligibility. This is being done to avoid upsetting participants and letting [name], a clinical psychologist, handle communication of more sensitive information. For participants who score a 20 or higher on the PHQ-8, they will be contacted via email to let them know they are ineligible and to provide them with a list of resources/support (attached in study documents) for their symptoms of depression if they want to utilize those options. It's important to note that a high score on the PHQ-8 only indicates the presence and severity of symptoms of depression, but not an actual diagnosis.

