Intervention. All participants will join an 8-week counselor-led (counselors go through the DPP lifestyle coach training) Diabetes Prevention Program (DPP) lifestyle intervention in a private Facebook group. Depending on which group participants are randomized to will determine which Facebook group they join. The DPP content will stay the same across all groups. Participants will also be asked to track their diet and exercise on MyFitnessPal as part of the program. Participants will be randomized into one of three groups that differ regarding dietary tracking. Group One will be called the **Daily Tracking Group** and will be asked to track their diet every day in the program. Group Two will be called the **1 On/1 Off Tracking Group** and will be asked to track every other week which would result in 4 weeks of tracking and 4 weeks off from

tracking. Finally, Group Three is called **2 On/1 Off Tracking Group** and will be asked to track for 2 weeks, then they will get a 1-week break and repeat that pattern until the end of the program.

Facebook groups with twice daily pre-programmed posts as in our previous studies (see 4 sample posts below).27,29,30,31 All Facebook groups will be on the "private" setting which means only group members can see the group and its content. Each week's content is based on the corresponding

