module of the DPP. The DPP assigns participants the goals of 1) calorie tracking to achieve a calorie goal based on amount needed to lose 1-2 pounds per week, 2) developing a healthy diet consistent with the American Heart Association guidelines, 3) engaging in 150-300 minutes per week of moderate/vigorous intensity exercise (i.e., brisk walk at 2.5-4 mph, bicycling, gardening, dancing, water aerobics, canoeing, playing doubles tennis. etc.) or 75-150 minutes of vigorous exercise (e.g., jogging at 6mph, soccer game, shoveling, playing a tennis singles game, etc.), 4) developing a strength training regimen consistent with the National Exercise Guidelines, and 5) losing 1-2 pounds per week. Goal setting happens on Mondays when the counselor posts diet and exercise goals with the group. The counselor will give the group different sets of 2 goals each week—a diet goal (e.g., reduce added sugar) and an exercise goal (e.g., add 15 minutes of moderate intensity exercise on 3 days) to help participants progress toward the overall program goals. On Fridays, the counselor posts a weigh-in post asking participants to reply with their weight change in pounds for the week. This ensures participants are weighing themselves weekly and allows an opportunity for problem solving for those not losing weight. Goal accountability happens each Sunday when the counselor posts asking participants to report how they did on the weekly goals. In between these recurring posts are posts that reflect the DPP module for the week (e.g., nutrition, making time for exercise). Many posts contain links to our Pinterest page which includes recipes, meal plans, and workouts tailored to dietary preferences (e.g., vegetarian) and cultural influences (e.g., African American,

Latinx). Participants also have the opportunity to send their counselor private messages if they don't want to post in the group. Additionally, the coach or study team members may post periodic videos of themselves or study-related content to facilitate building a relationship with the participants and to assist with stimulating engagement. The coach/study team will also post about MyFitnessPal to give them tips/tricks with their tracking and remind the relevant groups which weeks they are tracking and are not tracking. The counselors may attempt to re-engage any participants who stop commenting or reacting in the Facebook group by tagging them in a post, private messaging, emailing, or calling them.

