Follow-ups/Assessments: The follow-ups/assessments will occur at the 9 and 12-week marks after the intervention has begun. At the 9-week mark (the week after the program ends), participants will receive a link to an online REDCap survey. This survey will be a repeat of some of the measures assessed at baseline (indicated in the measures table below) and questions to solicit participants' feedback. Then, at both the 9 and 12-week assessments, the participants will also weigh in. At the 12-week assessment, we will also collect their MFP diary entries, but that does not require the participant to do anything. Participants will be compensated (compensation explained in Payment/Course Credit to Participants section) for completing these assessments.

Adverse Events: Adverse events will be documented during the intervention and assessments. AE's will be formally assessed during the 9-week assessment by asking questions in the REDCap survey. During the intervention, AE's will be documented when a participant reports it to the

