- Currently smokes or vapes nicotine twice a week or more
- Has a digestive disorder/condition that precludes dietary changes
- Meets criteria for severe depression on the PHQ-8 (score of >19)
- Does not currently own a smartphone
- Participated in previous weight loss studies under the PI
- Unable to attend the orientation webinar
- Had major surgery in past 6 months and have not been cleared by their doctor to resume physical activity and diet changes
- Plans to have major surgery in the next 6-months
- Has an implanted cardiac defibrillator or pacemaker
- Did not complete screening and on-board processes of study (screening survey, webinar, e-consent, baseline survey, app set-up, scale set-up, etc.)
- Is a student and/or staff of the PI.

Removal from Study

Describe the conditions under which participants may be removed from the study, e.g., noncompliance with study rules, study termination, etc. \Box N/A

Participants will be removed from the study if: 1) they do not complete all screening, baseline, and on-boarding procedures (two surveys, consent, webinar orientation, app set-up, and scale set-up, join the Facebook group), 2) become pregnant during the study period, 3) post threatening or disturbing content in the Facebook group (e.g., bullying/harassment of others, hate speech, violent/graphic content, violating privacy of others etc.), and 4) if they choose to withdraw their participation from the study. Participants reporting that they would like to

withdraw from the study will be given the option to 1) withdraw from all intervention-related activity and contacts, but still complete the final assessment or 2) withdraw from the study completely with no additional study contact. If a participant becomes pregnant during the study, they will be withdrawn from the intervention, but will be asked to complete the follow-up assessments.

Potential Harms/Risks and Inconveniences:

Describe the potential risks to participants (and secondary participants, if applicable) and *steps taken to minimize risks* for each participant population. For each risk, you must assess the likelihood of occurrence, and, if it were to occur, the associated severity. Types of risks to consider include, but are not limited to: physical, psychological, social, legal, employment, and financial.

N/A (no foreseeable risks anticipated) or,
Describe any anticipated inconveniences the participants may experience (such as
their time, abstention from food, etc.): \square N/A

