Have stopping rules been established for the study? ⊠ No ☐ Yes If yes, describe the stopping rules:
Are there defined criteria for when study interventions should be discontinued? $oxtimes$ No \Box Yes
If yes, describe the criteria:
Are there exams or procedures that the subject will be asked to have done or

follow to safely withdraw from the study? \boxtimes No \square Yes

If yes, describe the procedures for safe withdrawal of subjects (NOTE: Withdrawal procedures should also be described in the consent):

Privacy/Confidentiality:

Explain how the privacy interests of participants will be maintained during the study (note that privacy pertains to the individual not to the data):

For the initial screening survey, participants can answer the questions at their own pace and in an environment of their choice since it is done via a link online. If they do not want to finish, they can exit out of the survey whenever they would like. We also provide a simple information sheet prior to the survey so they can decide if they even want to move forward with doing the screening survey.

During the webinar process, UConn staff will go over all the details of the study and what it means to be a participant to give them a thorough description of what they can expect and what the study is so they can decide if this study is a good fit for them. During the webinar, they turn their video and audio off and choose where they view the webinar.

Most contact is done online so participants can control where they are and how they answer on their own time. They will have ample time to decide if they want to participate or not and ask UConn staff any questions they may have. Consent will also be done online so they can control where they are when reading the form as well as the amount of time they have to read through the form before deciding.

Participants will be informed in the consent form that they are able to withdraw from the study at any time for any reason without any consequences. They can skip questions during baseline and follow-up assessments if it makes them uncomfortable as well.

The participant can control when and where they use MyFitnessPal and Facebook group. We will encourage them throughout the study to use the app and the Facebook group as directed, but we only do so when it seems like they may be falling behind and if they do not reply to our contacts, we do not bother them about it again.

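### One removal ground, not joining the Facebook group, can act only after randomization, and follow-up of those it removes is not stated

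*Protocol*

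**What the plan says.** The first removal condition under Removal from Study is failure to complete the screening, baseline and on-boarding procedures, which it spells out as "two surveys, consent, webinar orientation, app set-up, and scale set-up, join the Facebook group".

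The order of events is set out under Design, Procedures, Materials and Methods:

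- Study Design: "Eligible participants will then complete an on-boarding process, which includes MyFitnessPal and scale set up", and after that "Participants will then be randomized (stratified by gender) and complete an 8-week intervention".
- Baseline: participants must finish both surveys, the webinar, consent, the scale set-up and a baseline weight, and must "set-up all study apps before being randomized into the trial". Facebook is not in this list.
- Intervention: "Depending on which group participants are randomized to will determine which Facebook group they join".

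On follow-up after someone stops, Removal from Study asks participants who become pregnant to complete the assessments, and lets those who ask to withdraw choose to complete the final one. The participant retention paragraph under Data Safety Monitoring offers follow-up to those who choose to drop the intervention. It also promises reminders of upcoming assessments in general terms. None of these texts names a randomized participant who never joins the group.

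**The concern.** An entry check applied before assignment costs a randomized comparison nothing. A removal rule applied after assignment takes people out of the randomized set because of something they did, or did not do, once their arm was fixed. Here a single item mixes the two kinds of step under the label of on-boarding.

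If staff apply the rule literally and treat removal as the end of contact, week 9 and week 12 data from randomized participants may be lost. Three planned outputs could be touched: retention, which is reported in each condition; adherence to the tracking prescription; and burden, which is compared between conditions by ANOVA. The sample size rests on feasibility, and failure to start the assigned programme is itself feasibility information.

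**Working it through.** The protocol gives no figure to reproduce. The check is mainly one of sequence.

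**Step 1: when each listed step happens**

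| Step in removal item 1 | Timing | Source |
|---|---|---|
| Two surveys, consent, webinar | Before randomization | Baseline |
| App set-up, scale set-up | Before randomization | Study Design; Baseline |
| Joining the Facebook group | After randomization | Intervention |

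The on-boarding list in Study Design and the matching exclusion criterion are both open-ended, so the absence of Facebook from them proves little. The ordering rests on the Intervention paragraph: a group determined by the arm cannot be joined before the arm is assigned.

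**Step 2: does follow-up depend on the group?** It does not. The scale and apps are in place before randomization. The week 9 survey is a REDCap link, and the weigh-ins use the participant's own scale. For the tracking data, "At the 12-week assessment, we will also collect their MFP diary entries, but that does not require the participant to do anything". Any loss would therefore be avoidable.

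**Step 3: possible size.** Inputs: 108 participants (Justification of Sample Size) and three arms (Intervention). Equal arms are an assumption, in line with the stated online groups of 36: 108 / 3 = 36. The number of non-joiners, k, is not given, so 1 to 3 per arm is assumed.

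Highest attainable retention with k unfollowed non-joiners kept in the denominator = (36 − k) / 36:

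- k = 1: 35/36 = 97.2%
- k = 2: 34/36 = 94.4%
- k = 3: 33/36 = 91.7%

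Each person costs 1/36 = 2.8 percentage points.

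The choice of denominator also matters. If 30 of 36 complete follow-up (assumed), retention is 30/36 = 83.3%. If three removed non-joiners are left out, it is 30/33 = 90.9%.

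**Step 4: burden.** The measures table attaches a 0-10 scale to the diet tracking acceptability items. Burden sits in a separate row with no scale, so no bound on the burden comparison can be calculated.

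**The case against.** The strongest reply is that follow-up is unstated, not forbidden. Pregnancy is also a removal condition, yet follow-up is then requested, so in this section removal does not by itself mean that assessments stop. The general reminders of upcoming assessments are not limited to group members. Retention is to be reported in a CONSORT diagram, which should make removals after randomization visible. Denominators are often left to an analysis plan, and one may exist. All of this stands, and it lowers the risk of unnoticed loss. It does not move the Facebook step to before randomization or say whether a non-joiner is invited. An analysis plan can define a denominator but cannot recover an assessment that was never requested.

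The numbers should also be small. Participants must already log in to Facebook on at least 5 days a week, and people unwilling to use it for the study are ruled ineligible. That leaves only those who agree, are randomized and then do not join.

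A reader might infer that the protocol contradicts itself by removing those who never join while keeping those who join and fall silent. The text does not support that. "The counselors may attempt to re-engage any participants who stop commenting or reacting in the Facebook group" concerns people already in the group, and "We will encourage them throughout the study to use the app and the Facebook group as directed" is privacy text about encouragement. Neither is a rule for someone who never enters, and the programme content is delivered in the group, so separating people who never started from people who went quiet is not inconsistent in itself.

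**Conclusion.** The point holds as a minor one. Part of a stated removal rule can act only after randomization, and the protocol does not settle the follow-up of the people it removes.

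The size is 2.8 percentage points of attainable retention per unfollowed non-joiner. This assumes equal arms of 36 and that the person stays in the denominator. How many there will be cannot be estimated from the protocol.

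Two stronger conclusions might be drawn, and neither is supported. One is that non-joiners are barred from the week 9 and week 12 assessments; the protocol is silent on this. The other is that the rule biases the comparison of arms; nothing shows that non-joining would differ by arm, and the effect on burden has no calculable bound. Weight change will not be compared by condition, so that comparison is not at stake.

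**What to change.** In Removal from Study, delete the Facebook step from the first item, so that it covers only steps completed before randomization. Treat not joining as non-adherence to the intervention. In the retention paragraph of Data Analysis, state that every randomized participant stays in the assigned arm's denominator. Invite non-joiners who have not refused contact to both assessments.

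If joining is meant as a condition of entry, it has to be checked before assignment and so cannot use the arm-specific group.

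The cost is a few words in two sections and invitations to a few people; no new device or survey is needed. Reported retention may be slightly lower. Gift cards come to at most $50 + $25 = $75 per additional completer (Payment/Course Credit to Participants). For an assumed 1 to 3 non-joiners in each of three arms, that is 3 × $75 = $225 to 9 × $75 = $675 in all.
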